### **17.4 Secondary hypotheses: Follow-up data**

- 1) A higher percentage of incentive than no incentive participants will test negative for all drugs of abuse and alcohol
- 2) Incentive participants will report less HIV risk exposure than no incentive
- 3) Incentive participants will report less criminal activity than no incentive.
- 4) Incentive participants will have lower scores on the BSI.
- 5) Incentive participants will have greater utilization of outpatient treatment services.
- 6) Incentive participants will have less utilization of detoxification and ER services.
- 7) There will be no differences between groups on measures of gambling.
- 8) There will be no differences between groups on measures of employment.

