duration of stimulant-free testing). Follow-up interviews and urine testing will also be obtained from all subjects who sign informed consent, whether or not they stay in treatment for 12 weeks (“intent-to-treat” sample). Subjects will be assessed at all follow-up visits (1, 3, and 6 months) for: 1) drug use via full screen urinalysis and alcohol breathalyzer, 2) drug use via self-report, 3) HIV risk exposure, 4) employment status, 5) criminal activity, 6) gambling behavior, and 7) psychiatric symptoms. It is predicted that outcomes for those assigned to receive incentives in addition to standard care will be better than outcomes for those who receive standard care only. Specifically, those who receive incentives will have less drug use and criminal activity, more employment and fewer psychiatric symptoms.

**SUBJECT BENEFITS:** All study participants will receive compensation of \$25 for each follow-up assessment completed. All participants may benefit from stopping their drug use during treatment and working toward life-style changes that are needed to sustain long-term abstinence. Those in the incentive condition may experience enhanced motivation to abstain and may benefit from the tangible incentives received.

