## **9 PROJECTED STUDY SAMPLE SIZE: 400**

One perspective on sample size was obtained by conducting a power analysis based on data from Piotrowski et al. (1999). This study implemented a complex incentive intervention at a community VA methadone clinic that targeted multiple drugs of abuse. Although the specific intervention was quite different from the one proposed in the current CTN protocol, this was an incentive study conducted in a community clinic with considerable variability in outcome. With probability of a Type I error set at 0.05 (alpha) and a Type II error set at 0.20 (Power = 0.80), and using a two-tailed test, it was determined that 130 subjects would be needed in the incentive and control groups, respectively, to obtain statistical significance on the measure percent drug negative urines (28.5% versus 16.3% during months 5 and 6).

Additional sample size estimates have been calculated based on two recently published voucher incentive studies, one of which did (Preston et al., 2000) and one of which did not (Downey et al., 2000) detect statistically significant effects of the voucher intervention being tested. Effect sizes for the primary outcome variable percent drug-free urines ranged from .16 to .19 with a mean of .18. This yielded sample size estimates of 110-153. In addition, these estimated sample sizes have been adjusted based on 10% to 20% increases in variability due to multi-site testing. As shown in the appended table, our projected sample size of 200 per group should allow us to detect between group differences of the magnitude previously observed with power = .80 and alpha = .05, even with a 20% increase in variability over single-site studies.

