Marked increase in gambling behavior. The variable ratio schedule proposed includes an element of chance, and there is some concern that this will stimulate gambling behavior in those who have a problem with this type of impulsive behavior. It should be noted that there is no evidence to support such a concern. Further, the variable ratio incentive procedure itself could not be defined as gambling. It does not require the volunteers to put up their own money, nor is there any chance that volunteers could benefit excessively or lose their own money as a result of participating successfully in the incentive program. There is a chance that an individual with a gambling problem in remission could be stimulated to resume gambling. For this reason, compulsive gambling in remission has been added as a study exclusion criteria. There is also a chance that individuals who tend to engage in excessive gambling and who abstain from drug use during the study would have more disposable income to spend on gambling. For this reason, gambling behavior will be monitored at study follow-up points. A substantial increase in self-reported gambling behavior at 1, 3 and 6 months compared with baseline will be reported as an adverse event. The changes needed to trigger an adverse event evaluation is an increase of 10 days or more per month on which gambling occurred (e.g. from 10 to 20 days), a 50% or greater increase in the reported amount of money spent on gambling and an absolute amount spent of at least \$100 per month. Any subject who meets these criteria will be given a clinical interview regarding their gambling behavior in relation to other changes in life circumstances. The adverse event report will include a judgement by the clinician regarding the extent to which the behavior change might have been protocol-related. Information about gambling behaviors reported by study subjects will be provided to counselors so that they can work on this independent behavior problem with their clients, as appropriate. Subjects may be withdrawn from the study protocol and referred for specialized gambling treatment if clinically indicated.

Hospitalization. An adverse event will be reported for any hospitalization episode. Drug overdose requiring medical intervention will be tracked separately. Overdose is a serious risk among drug abusers in general, but may be of particular concern when patients have abstained for any substantial period of time.

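### Section 17.4 hypothesises no differences on gambling and employment, which difference tests without a margin cannot support, and the Summary predicts more employment

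*Protocol*

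**What the plan says.** Protocol section 17.4 lists eight secondary hypotheses for the follow-up data. Six predict a direction. Item 7 reads "There will be no differences between groups on measures of gambling" and item 8 reads "There will be no differences between groups on measures of employment".

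The opening of section 16 says that the section gives the approaches used to test the study hypotheses. For continuous outcomes, section 16.4 names t-tests, multiple regression, repeated measures analysis of variance and mixed models. For dichotomous outcomes it names chi-square, logistic and Poisson regression. For outcomes measured at several time points it proposes GEE. It promises 95% limits for hazard ratios, relative risks and odds ratios, but none for a difference in means. The gambling and employment outcomes listed in section 16.3 are counts of days in the past 30. No margin and no rule for concluding that the groups do not differ appears anywhere.

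Section 18.1 makes increased gambling one of three reportable adverse event types, beside death and hospitalization. It says of the chance element in the prize schedule that "there is some concern that this will stimulate gambling behavior" in people with a problem of this kind.

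The Protocol Summary (section 2, Efficacy Assessments) predicts that the incentive group will have "less drug use and criminal activity, more employment and fewer psychiatric symptoms".

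**The concern.** A difference test starts from the assumption of no difference and can only reject it. When the study hypothesis is itself that there is no difference, the test can refute it but never support it. A non-significant p-value arises both when the groups are alike and when the data are too imprecise to tell, and without a margin the plan cannot separate the two.

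For gambling, the protocol takes the possibility of an increase seriously enough to exclude people in recovery from gambling, to monitor gambling at each follow-up, and to report substantial increases as adverse events. A statement that a chance-based prize procedure leaves gambling unchanged is therefore one that readers will look for, and the plan has no valid route to it.

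Employment has a second problem. The Summary and section 17.4 predict different things, so a significant benefit would agree with one and a null result with the other.

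**Working it through.** **Inputs from the protocol.** Two-sided alpha 0.05, power 0.80, 200 per group (section 9); 95% interview completion in past experience (section 13); as many as 1000 participants (section 18). The protocol gives no SD for gambling days, so results are in SD units.

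**The plan's own sample size, as a check.** Section 9 says: "Effect sizes for the primary outcome variable percent drug-free urines ranged from .16 to .19 with a mean of .18", and derives estimates of 110-153, read here as per group. Taking the effect size as Cohen's f, so that d = 2f, n per group = 2 × (1.960 + 0.842)² / d² = 15.70 / d².

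- f = .16, d = .32: 15.70 / 0.1024 = 153.3, so 154
- f = .18, d = .36: 15.70 / 0.1296 = 121.1, so 122
- f = .19, d = .38: 15.70 / 0.1444 = 108.7, so 109

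The stated range reproduces to within one participant. It concerns percent drug-free urines. No power statement covers gambling or employment.

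**Precision for a difference in means at 200 per group.**

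- Standard error = √(2/200) = 0.100 SD.
- Half-width of the 95% interval = 1.96 × 0.100 = 0.196, about 0.20 SD.
- Difference detectable with 80% power = 2.802 × 0.100 = 0.28 SD.

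**Chance that a true increase is non-significant**, 1 − Φ(δ/0.100 − 1.96):

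| True increase | Power | Non-significant |
|---|---|---|
| 0.10 SD | 17% | 83% |
| 0.15 SD | 32% | 68% |
| 0.20 SD | 52% | 48% |
| 0.25 SD | 71% | 30% |
| 0.30 SD | 85% | 15% |

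**Sensitivity to sample size, at 0.20 SD.**

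- 190 followed per group (200 × 0.95): standard error √(2/190) = 0.103, half-width 0.20 SD. Power Φ(0.20/0.1026 − 1.96) = Φ(−0.01) = 50%, so about 50% missed.
- 500 per group (1000 enrolled): standard error √(2/500) = 0.063, half-width 0.12 SD. Power Φ(0.20/0.0632 − 1.96) = Φ(1.20) = 88%, so about 12% missed.

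**A dichotomous gambling outcome, with assumed rates.** At 200 per group, 5% versus 10% has power of about 48%, and 2% versus 4% about 22%.

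**Could the trial support a claim of no increase?** If the true difference is zero and the upper 95% limit must lie below a margin m, the chance of success at 200 per group is Φ(m/0.100 − 1.96): 52% for m = 0.20 SD, 71% for 0.25 SD, 85% for 0.30 SD and 94% for 0.35 SD. These show what the sample size can bear. They are not proposed margins.

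**Employment.** No arithmetic is needed. The Summary's prediction of more employment and item 8 of section 17.4 are both current text, and only one can be the prespecified prediction.

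**The case against.** Several points on the other side stand.

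- The protocol nowhere says that a non-significant p-value will be taken as proof. A reader might infer that rule, because a difference test is the only tool offered, but it is not written. The same holds for the inference that a real increase would be reported as safe. Section 18.1 requires gambling to be compared with baseline at 1, 3 and 6 months, and a large individual rise in days and spending leads to an adverse event report and a clinical interview whatever the group comparison shows. That trigger does not, however, test whether the groups differ.
- A reader might call gambling the trial's main safety concern. The protocol does not. It lists gambling with death and hospitalization, says that there is no evidence for the concern, and calls overdose a serious risk.
- Interval estimates are partly planned: relative risks and odds ratios carry 95% limits. Without a margin these still give no rule for concluding no difference.
- It is tempting to state the miss rate in days and to name a margin in days. The documents support neither. The only gambling-day threshold is the individual trigger of 10 days or more, which is not a group margin.
- Baseline adjustment and GEE over three follow-ups could narrow the interval, and enrolment may exceed 400.
- Margins are often left to a statistical analysis plan, which was not available here. But this protocol states both the hypothesis and the tests, and the two do not fit.
- To call the employment conclusion undefined would go too far. The outcome and methods are given; only the predicted direction conflicts.

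**Conclusion.** The point holds for both outcomes. Items 7 and 8 are null statements paired with methods that cannot support them. At the planned 200 per group, a true increase of 0.20 SD would be non-significant about 48% of the time, and the 95% interval would reach about 0.20 SD either side of the estimate. These figures assume an unadjusted comparison of means at one follow-up, a normal approximation and full follow-up. Enrolling 1000 would cut the miss rate to about 12%, but would not make non-significance evidence of no difference. The employment contradiction is a matter of text and rests on no assumption.

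Both are secondary hypotheses. The primary outcomes, sample size and data collection are untouched, so this should be corrected but does not threaten the trial's main conclusion.

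**What to change.** In section 17.4, restate item 7 as an estimate: the incentive-minus-control difference in gambling days in the past 30, with its 95% confidence interval. State that a non-significant test will not be taken as showing that the groups do not differ. Claim no increase only if the upper limit lies below a margin that the sponsor justifies and fixes before data are seen. If no margin can be justified, report the estimate and interval without that claim. Add to section 16.4 that differences in means carry 95% intervals.

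For employment, use one hypothesis in both the Summary and section 17.4, tested two-sided and reported with its 95% interval.

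The cost is wording and one margin, with no new data or visits. The downside is that the gambling result may have to be reported as inconclusive.

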## 18 HUMAN SUBJECTS

A minimum of 400 and as many as 1000 individuals applying for treatment at community drug abuse clinics will participate in this study. Recruitment for the study will take place during the clinic intake process. Inclusion criteria ensure that the study sample are cocaine or methamphetamine users. The sample is inclusive of community treatment participants; the only exclusion criteria proposed is inability to comprehend the consent form, based on clinical judgement of acute psychosis or intoxication.

### 18.1 Risks

The risks of this study are minimal and are described below. Adverse events will be reported only for death, hospitalization and increase in gambling behavior, as defined below.

Dissatisfaction with study assignment. One risk is that participants randomly assigned to the no incentive condition will be dissatisfied with their assignment. This is a risk common to many randomized clinical trials, particularly where interventions cannot be blinded. The risk is explained as part of the consent procedure, and those unwilling to take the risk of assignment to control condition can refuse to participate. Experience of the Co-lead Investigator, who has conducted similar trials in community clinics, is that assignment dissatisfaction has not been a major problem.

Drug use following receipt of large prizes. Participants randomly assigned to the experimental incentive group will be able to earn small, large and jumbo incentive items under a variable ratio schedule as rewards for submitting drug-free urines. There is some risk that clients who have been abstinent would return to drug use following receipt of a large (\$20) or jumbo (\$80) prize. This is included as a risk due to concern that study patients may sell prize items and use the money to purchase drugs. The percentage of large and jumbo prize awards that are followed by drug use (i.e. a positive urine at the next study visit) will be reported, and compared if possible with return to drug observed on occasions when only small prizes or no prizes have been received. It should be noted that any detrimental effect of the protocol with regard to stimulating relapse is self-limiting, as clients can no longer earn incentives while actively using drugs.

Marked increase in gambling behavior. The variable ratio schedule proposed includes an element of chance, and there is some concern that this will stimulate gambling behavior in those who have a problem with this type of impulsive behavior. It should be noted that there is no evidence to support such a concern. Further, the variable ratio incentive procedure itself could not be defined as gambling. It does not require the volunteers to put up their own money, nor is there any chance that volunteers could benefit excessively or lose their own money as a result of participating successfully in the incentive program. There is a chance that an individual with a gambling problem in remission could be stimulated to resume gambling. For this reason, compulsive gambling in remission has been added as a study exclusion criteria. There is also a chance that individuals who tend to engage in excessive gambling and who abstain from drug use during the study would have more disposable income to spend on gambling. For this reason, gambling behavior will be monitored at study follow-up points. A substantial increase in self-reported gambling behavior at 1, 3 and 6 months compared with baseline will be reported as an adverse event. The changes needed to trigger an adverse event evaluation is an increase of 10 days or more per month on which gambling occurred (e.g. from 10 to 20 days), a 50% or greater increase in the reported amount of money spent on gambling and an absolute amount spent of at least \$100 per month. Any subject who meets these criteria will be given a clinical interview regarding their gambling behavior in relation to other changes in life circumstances. The adverse event report will include a judgement by the clinician regarding the extent to which the behavior change might have been protocol-related. Information about gambling behaviors reported by study subjects will be provided to counselors so that they can work on this independent behavior problem with their clients, as appropriate. Subjects may be withdrawn from the study protocol and referred for specialized gambling treatment if clinically indicated.

Hospitalization. An adverse event will be reported for any hospitalization episode. Drug overdose requiring medical intervention will be tracked separately. Overdose is a serious risk among drug abusers in general, but may be of particular concern when patients have abstained for any substantial period of time.

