### **6.2 Bonus incentive targets: opiates**

In methadone clinics, only opiates will be used as the bonus drugs. Clinicians will receive information on marijuana use by their patients, but marijuana is not included as a bonus drug for methadone settings. This is because marijuana is not traditionally included in these settings when determining drug-free status for clinic privileges such a take-home medication.

Testing positive on a bonus drug does not preclude receipt of incentives for primary drug targets.

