### ***Escalating Schedule of recovery picks for primary drug abstinence***

Clients in the incentive group will earn at least one recovery pick for each sample submitted that tests negative for the primary drugs: cocaine, amphetamine, methamphetamine and provided a negative breath alcohol reading is obtained. The number of picks allowed at each

urine collection will escalate with consecutive week of negative testing on primary drugs. Specifically, an additional recovery pick is added for each consecutive week that the participant tests negative for cocaine, amphetamine, methamphetamine and alcohol.

Study week	Number of recovery picks for primary drug abstinence
1	1
2	2
3	3
4	4
5	5
etc	

Missing or positive samples result in reset to 1 in number of recovery picks for the next negative sample submitted.

The escalating schedule is designed to sustain long periods of abstinence, and as such, the highest rates of reinforcement are scheduled late in the protocol for continuously abstinent participants. In order to counteract discouragement from the low reinforcement rate expected early in the escalating draw protocol, a single \$20 bonus incentive will be given after two consecutive weeks of abstinence from primary target drugs. This bonus incentive can only be received once during the study; if a client re-sets and starts the escalating schedule over again, no bonus incentive will be available.

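### Section 18.1 counts only a positive urine as drug use after a large or jumbo prize: absence is tallied as no use, alcohol cannot be detected, and the drugs that count are not named

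*Protocol*

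**What the plan says.** Section 18.1 describes the risk this way: "There is some risk that clients who have been abstinent would return to drug use" after winning a large ($20) or jumbo ($80) item, because the item might be sold to buy drugs. The planned measure, which will be reported, is this: "The percentage of large and jumbo prize awards that are followed by drug use (i.e. a positive urine at the next study visit"). It is to be "compared if possible with return to drug observed on occasions when only small prizes or no prizes have been received". The paragraph adds that any harm limits itself, since "clients can no longer earn incentives while actively using drugs".

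Other sections bear on what this measure can capture:

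- Section 6.1 makes alcohol a primary target alongside cocaine, amphetamine and methamphetamine. Section 11.4 detects it by breathalyzer. The urine cup covers cocaine, amphetamine, methamphetamine, morphine and THC.
- Section 6.2 states that "Testing positive on a bonus drug does not preclude receipt of incentives for primary drug targets", and that "marijuana is not included as a bonus drug for methadone settings".
- Section 11.5, under the escalating schedule, states: "Missing or positive samples result in reset to 1 in number of recovery picks for the next negative sample submitted".
- Section 11.4 treats an unreplaced invalid specimen as missing, and as positive only for incentive procedures.
- Section 16.5 says replacing missing data should generally be unnecessary. It sets an imputation rule for one measure, longest duration of abstinence.
- Section 11.3 keeps participants active whatever their attendance, provided they remain enrolled at the clinic. Section 11.4 lets an absentee give the sample on the next attendance.

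**The concern.** The event definition does not match the risk it is meant to measure. The risk is a return to use by someone who was abstinent. The event is one type of test result at one visit, with no rule for the case where the test does not happen and no list of the drugs that count. The definition is introduced by an i.e., so the protocol fixes it rather than leaving it open.

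Section 18.1 limits adverse event reporting to death, hospitalization and increased gambling. Relapse after a prize is therefore not an adverse event, and this percentage is the only measure the protocol plans for it. If it is too low, a harm specific to the incentive procedure is understated. If it includes people whose use never changed, it is too high and the comparison with small-prize and no-prize occasions is diluted. A reader given only the percentage could not tell which had happened.

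**Working it through.** The protocol states no figure for this measure, so there is nothing to reproduce. The check sets the rules side by side and then shows how far the measure could move under assumed rates.

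**Step 1: does any missing-data rule reach this measure?** The reset in section 11.5 governs the number of picks. The invalid-specimen rule in section 11.4 counts as positive only for incentive procedures. The imputation in section 16.5 covers only longest duration of abstinence. None applies to section 18.1. With all awards as denominator and a positive urine as numerator, an award with no urine afterwards is a non-event.

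**Step 2: what does the next study visit mean?**

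- Next scheduled: any no-show is a non-event.
- Next attended: a participant who returns still positive is counted, one who returns clean is not, and one who never returns is not.

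A participant who wins, uses and does not come back is missed on both readings.

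**Step 3: effect of absence (assumed rates).** Let u be the share of awards truly followed by use, and m the share of those users who give no later urine that counts. Everyone else is assumed to attend. As a share of all awards, the measure reads u × (1 − m). As a share of awards with a urine, it reads u(1 − m) / (1 − um). With u = 20%:

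- m = 30%: 14% of all awards; 14/94 = 14.9% of awards with a urine
- m = 50%: 10%; 10/90 = 11.1%
- m = 70%: 6%; 6/86 = 7.0%

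With u = 30% and m = 25%, 50% or 75%, the all-awards figures are 22.5%, 15.0% and 7.5%. Restricting the denominator to awards with a urine barely helps (24.3%, 17.6%, 9.7%).

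On the next-attended reading, suppose half of the users miss the next scheduled test and a share r of those come back still positive. The measure then reads 20% × (1 − 0.5 × (1 − r)): 10% if r = 0, 15% if r = 0.5, and 20% if r = 1.

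**Step 4: alcohol.** Alcohol is not on the urine panel, so a return to drinking alone contributes nothing to the numerator at any rate.

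**Step 5: unnamed drugs.** Picks for primary abstinence depend only on stimulants and alcohol. Extending the section 11.5 schedule to week 12 at two tests a week, a participant negative on every primary target throughout earns 2 × (1 + 2 + … + 12) = 156 picks, even if opiate-positive at every test. The chance of a large or jumbo chit is 8% + 0.2% = 8.2%, so 156 × 0.082 = 12.8 such prizes are expected, before the one-off bonuses. The expected number of visits with at least one is the sum over weeks w = 1 to 12 of 2 × (1 − 0.918^w) = 9.6 of 24.

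If any panel drug makes a urine positive, each of these awards followed by a urine would count as drug use with nothing changed. With a share q of awards going to such participants and true primary-drug relapse of 20% in the rest (assumed), the measure reads q + (1 − q) × 20%: 28%, 44% or 60% for q = 10%, 30% or 50%. Because the same people are also positive on small-prize and no-prize occasions, a true 10-point difference shrinks to (1 − q) × 10 = 9, 7 or 5 points. If only primary drugs count, this effect vanishes, but the alcohol gap in step 4 remains.

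**The case against.** The strongest reply is that this is a descriptive percentage in the Human Subjects section. It is not a hypothesis in section 17, a listed outcome in section 16 or an adverse event trigger, and tabulation details are commonly left to an analysis plan that is not shown here. Absence is also captured by retention and by the share of scheduled urines given (section 16.2), and overdose is tracked separately. Much of this stands, and it limits the importance of the point. But the protocol does not leave the event open, and none of those other measures is tied to prize awards.

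Four stronger readings are tempting, and the documents do not support them:

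- *Participants positive for opiates or marijuana throughout are counted as relapses.* Section 18.1 names no drug. Its language of return to use, its remark that "clients can no longer earn incentives while actively using drugs" and the shorthand positive samples in section 11.5 all fit the primary drugs better. Such participants may be counted; the text does not say that they are. They would also dilute the comparison rather than create a false signal of harm.
- *The plan generally scores missing tests as positive and departs from that here.* Section 16.5 points the other way: no replacement is the general rule and longest duration of abstinence is the exception.
- *Because missing and positive samples have the same effect on picks, relapse will show as absence.* Equal consequences imply indifference, not avoidance. The protocol gives no data on attendance after relapse, and section 12 has counselors encourage continued samples.
- *Every user who misses a test is lost to the measure.* On the next-attended reading, those who return still positive are counted.

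**Conclusion.** The point holds in a limited form. As written, section 18.1 tallies an award followed by absence, an unreplaced invalid specimen or dropout as not followed by drug use, and cannot register a return to alcohol. Both features push the percentage down. It also leaves open which drugs make a urine positive. If all panel drugs were used, unchanged opiate or marijuana use would push the percentage up and weaken the comparison.

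The size cannot be derived from the documents. The illustrative drop from 20% to between 14% and 6% assumes both the relapse rate and the share of users with no later urine that counts, and the rise to between 28% and 60% assumes the less natural any-drug reading. Only the pick arithmetic (156 picks, about 12.8 expected large or jumbo prizes) rests on the protocol's own schedule, for a participant who is negative on primary targets throughout. What is affected is the interpretability of one descriptive safety figure; the efficacy conclusions are not.

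**What to change.** In section 18.1, define the event as a positive result for a primary target (cocaine, amphetamine or methamphetamine in urine, or a breath reading above 0.00) at the next scheduled test after the award. Report missed or unreplaced invalid next tests as a separate category. Add a sensitivity analysis that counts them as positive, rather than building that assumption into the main figure. Apply the same definition to the small-prize and no-prize comparison occasions.

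The cost is a few lines of wording and a little more tabulation. Prize records and the twice-weekly urine and breath results are already collected, and no visit or treatment rule changes. Some missed tests will have causes other than drug use, which is why they should be shown separately.
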